STATISTICAL ANALYSIS PLAN

Written Exposure Therapy to Reduce PTSD Symptoms in Survivors of Acute Cardiovascular Events: A

Pilot Randomized Trial

National Clinical Trial (NCT) Identified Number: NCT03605693

Principal Investigator: [name], MPH

Sponsor: Columbia University Irving Medical Center

Grant Title: Columbia Roybal Center for Fearless Behavior Change

Grant Number: P30 AG064198

Funded by: National Institute on Aging

Version Number: v.2.1

10 July 2020

STATISTICAL DESIGN AND POWER

Statistical Hypotheses

1. The majority ($\geq 50\%$) of acutely distressed survivors of CVD events who are eligible for our RCT will agree to be enrolled into a randomized trial of Written Exposure Therapy (WET) versus usual care.
2. It is feasible to complete 30-day outcome assessments for the vast majority ($\geq 80\%$) of participants.
3. A majority of intervention participants (≥ 6 of 10) will complete the majority (≥ 3 of 5) of WET sessions.

Primary Feasibility Endpoints

1. Proportion of acutely distressed CVD event survivors eligible for our RCT who agree to be enrolled into a randomized trial of WET.

Primary Efficacy Endpoint

1. PTSD Checklist - Stressor Specific (PCL-S) score [Time Frame: 1 month after hospital discharge]

This is to measure PTSD symptoms due to the index cardiovascular event. The PCL-S is self-report measure of the symptoms of PTSD. Respondents rate how much they were bothered by a symptom on a 5-point scale ranging from 1 (not at all) to 5 (extremely). The PCL-S (specific) asks about symptoms in relation to an identified stressful experience. The PCL-S aims to link symptom endorsements to the index cardiovascular event

Secondary Endpoints:

- Number of subjects completing the written exposure therapy [Time Frame: Approximately 1 month after hospital discharge]
This is to measure the feasibility of the therapy - completion to all 5 sessions among participants assigned to the intervention group
- Adherence to cardiovascular medications [Time Frame: Approximately 1 month after hospital discharge]
This is measured by the scoring from the voils adherence questionnaire (3-items).
- PHQ-8 score [Time Frame: Baseline, 1 month after hospital discharge]
This is to measure change in depressive symptoms. The eight-item Patient Health Questionnaire depression scale (PHQ-8) is established as a valid diagnostic and severity measure for depressive disorders in large clinical studies. Scores range from 0 - 24 and a score of 10 or greater is consistent with at least moderate depressive symptoms.
- Short Form health survey Version 2.0 (SF-12v2) score [Time Frame: Approximately 6 months after hospital discharge]
This is to measure quality of life. A health survey that uses 12 questions to measure functional health and well-being from the patient's point of view.

Sample Size and Power Estimates

As this is a pilot study, our sample size was guided by the need to enroll enough participants to examine the feasibility of conducting a larger scale trial of our intervention. In particular, we wanted to ensure that we were capable of recruiting, retaining, and assessing participants as well as implementing the desired intervention. Based on this goal, we estimated we needed to randomize 20 participants (10 per group) into the study. We felt that it was essential to include a randomization arm as this will give more realistic estimates of patients'

willingness to participate in a randomized experiment of this intervention being delivered in a novel context (for prevention and for those with CVD-event PTSD)—information that will be helpful for planning the larger study.

Statistical Analyses

General Approach. For descriptive statistics, categorical data will be presented as percentages and continuous data will be presented as means with standard deviations for normally distributed measures and as median with interquartile range for measures that are not normally distributed. Checks of assumptions (e.g., normality) underlying statistical procedures will be performed and corrective procedures will be applied (e.g., log transformation or nonparametric tests).

Missing Data. Our primary strategy for preventing missing data will be to invest in collecting data as completely as possible. We will carefully design our instruments and train our research coordinators to prevent/minimize dropout and collect all data completely. Data from in-person visits will be collected via iPads using an electronic data capture system (Filemaker) which will minimize loss of data and data entry costs. We will conduct weekly queries of the database to monitor for missing data.

Analysis of the Primary and Secondary Outcomes.

Primary Statistical Analyses for Feasibility Outcomes. We will use descriptive statistics to describe our participants and their outcomes; to determine the proportion of participants needed-to-screen; the proportion who complete 1-month follow-up without loss-to-follow-up; and the proportion who adhere to the WET intervention.

Statistical Approach for Efficacy Outcomes. All randomized participants will be analyzed according to the group to which they are assigned (i.e., intent-to-treat principle; ITT). All participants will be followed for 1 month.

Baseline Descriptive Statistics. Given this is a pilot feasibility design, there is no reason to compare key characteristics of patients randomized to the intervention versus control arms and assess whether the randomization happened to result in group differences.

Planned Interim Analyses. Given the relatively small sample size of this study (N=20 participants) and the expected minimal risk of written exposure therapy, interim analyses will not be planned

Subgroup Analyses. Given this is a pilot feasibility study, we will not conduct any pre-planned subgroup analyses.

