Targeting patients at increased risk of PTSD may be a more efficient approach to targeting PTSD preventive interventions, and initial research supports this notion. For patients with cardiovascular event-induced PTSD, several key predictors of PTSD symptoms at 1-month after the index event have been observed in our samples. Most notably and consistent with the broader research on PTSD triggered by more external traumatic events, both elevated threat perceptions at the time of ED presentation and elevated early PTSD symptoms as measured by the ASD scale (ASDS) within days after the cardiac event have been associated with increased PTSD risk. Accordingly, we will screen patients for elevations in threat perceptions and ASD symptoms to determine eligibility, similar to what has been done in other early PTSD intervention work.

To test our hypothesis that it is feasible to conduct a randomized trial of written exposure therapy, we propose to enroll 20 patients who are hospitalized for a CVD event, either ACS, stroke, TIA, or cardiac arrest. We will leverage the recruitment infrastructure of the REACH-Stroke, REACH-ACS, and REACH-Arrest studies (IRB protocols: IRB-AAAR8497) to identify possible participants for this trial, and to conduct baseline and 1-month follow-up assessments. Patients will first be screened for: 1) threat perceptions in the ED for ACS and stroke/TIA patients or upon hospitalization for cardiac arrest patients and 2) ASD symptoms within days of their enrollment in the study. Those with elevated threat perceptions and/or ASD symptoms will be randomized to 1) written exposure therapy (INT); *N*=10 or 2) usual care (CTR); *N*=10.

Specific Aim. To determine the feasibility of conducting a randomized trial of written exposure therapy in survivors of acute CVD events.

Feasibility Hypothesis 1. We can enroll and randomize 20 hospitalized CVD patients at NYP into randomized trial.

Feasibility Hypothesis 2. A majority of participants (>=7 of 10) assigned to the intervention will attend the majority (>=4 of 5) intervention visits.

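### The SAP sets thresholds for uptake, 30-day assessment and session completion but plans only percentages; a result that just meets a threshold cannot exclude rates well below it.

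*SAP*

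**What the plan says.** Under Statistical Hypotheses the SAP gives three thresholds.

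- **Uptake:** at least 50% "of acutely distressed survivors of CVD events who are eligible for our RCT will agree to be enrolled into a randomized trial". This is also the only item listed under Primary Feasibility Endpoints: "Proportion of acutely distressed CVD event survivors eligible for our RCT who agree to be enrolled into a randomized trial of WET".
- **Assessment:** "It is feasible to complete 30-day outcome assessments for the vast majority", with the threshold set at 80% or more.
- **Session completion:** "A majority of intervention participants", set at 6 or more of 10, will complete at least 3 of 5 sessions.

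Protocol section 1, Feasibility Hypothesis 2, sets a different adherence rule: "A majority of participants (>=7 of 10) assigned to the intervention will attend the majority (>=4 of 5) intervention visits". The SAP's secondary endpoints add a third definition, completion of all 5 sessions.

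The analysis is descriptive. The SAP's General Approach says that "categorical data will be presented as percentages". Its paragraph on feasibility outcomes lists a needed-to-screen proportion, then "the proportion who complete 1-month follow-up without loss-to-follow-up; and the proportion who adhere to the WET intervention". The Analyses paragraph in protocol section 2 is also descriptive and adds satisfaction. Neither document mentions a confidence interval or a precision target for any feasibility proportion, or a rate that would count as infeasible.

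**The concern.** The feasibility proportions are meant to be used. Protocol section 1 (Significance) says that, if feasibility is shown, the data will support grant applications for a powered trial. Both sample-size sections say that randomizing gives more realistic estimates of willingness to take part, for use in planning that trial. An estimate used for planning needs a statement of its uncertainty.

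The protocol accepts this for treatment effects: it gives no power calculation because small pilots estimate effects too imprecisely. It does not extend that caution to proportions from the same few patients. In its General Approach the SAP pairs means with standard deviations and medians with interquartile ranges, but gives proportions no accompanying measure of precision. Thresholds presented as statistical hypotheses and reported as bare percentages invite a met/not-met reading that 10 or 20 patients, or some 40 eligible patients, can support only weakly.

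**Working it through.** **Inputs**

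- Sample size (SAP, Sample Size and Power Estimates): "we estimated we needed to randomize 20 participants (10 per group) into the study". No formula lies behind it, so there is nothing to reproduce beyond 10 + 10 = 20.
- Assessment threshold: 0.80 × 20 = 16, so 16 of 20.
- Session completion: 6 of 10 (SAP) or 7 of 10 (protocol).
- Uptake: the number of eligible patients is not stated. Assumption: 20 enrol. The 50% threshold is then met if at most 20 / 0.50 = 40 were eligible, so the boundary case is 20/40.

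**Step 1. Intervals when a threshold is just met**

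For x successes in n, the Clopper-Pearson 95% limits are the 0.025 quantile of Beta(x, n − x + 1) and the 0.975 quantile of Beta(x + 1, n − x). Wilson limits are a check.

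| Result | Observed | Exact 95% CI | Wilson 95% CI |
|---|---|---|---|
| 6/10 (SAP adherence) | 60% | 26.2% to 87.8% | 31.3% to 83.2% |
| 7/10 (protocol adherence) | 70% | 34.8% to 93.3% | 39.7% to 89.2% |
| 16/20 (assessment) | 80% | 56.3% to 94.3% | 58.4% to 91.9% |
| 20/40 (uptake, assumed denominator) | 50% | 33.8% to 66.2% | 35.2% to 64.8% |

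If fewer patients are eligible, the exact uptake interval is 47.2% to 82.7% at 20/30 and 59.3% to 93.2% at 20/25. If recruitment stops at the 20th consent, the lower limit at 20/40 does not change, because needing at most 40 eligible patients is the same event as at least 20 consents among 40.

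**Step 2. Chance of meeting each rule at assumed true rates**

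The documents give no true rates, so those below are assumptions. The formula is P(X ≥ k) = Σ C(n, j) p^j (1 − p)^(n − j), summed from j = k to n. For example, with n = 10, k = 6 and p = 0.5: (210 + 120 + 45 + 10 + 1) / 1024 = 386 / 1024 = 37.7%.

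| Rule | Chance of meeting it at an assumed true rate |
|---|---|
| ≥6/10 | 4.7% at 30%; 16.6% at 40%; 37.7% at 50% |
| ≥7/10 | 1.1% at 30%; 5.5% at 40%; 17.2% at 50% |
| ≥16/20 | 5.1% at 60%; 11.8% at 65%; 23.8% at 70% |
| ≥20/40 | 3.6% at 35%; 13.0% at 40%; 31.6% at 45% |

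**Step 3. What a lower limit at the target would take**

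For the exact lower limit to exceed 50% with n = 10, 9 of 10 must complete (lower limit 55.5%). For it to reach 80% with n = 20, all 20 must be assessed (83.2%).

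**The case against.** The strongest reply is that this is a descriptive pilot. It needs no test and no larger sample, and any reader given the counts can compute an interval. The General Approach sentence is a default for all categorical data and does not forbid intervals. The rules also seldom pass when true rates are clearly poor: 6 of 10 is met about 5% of the time at a true 30%, and 16 of 20 about 5% of the time at 60%.

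Most of this stands. No test, power calculation or larger sample is called for. But an interval is itself a descriptive statistic, and naming it in advance keeps its reporting from depending on how the results look.

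Some stronger readings are tempting, and the documents do not support them.

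- **Every feasibility hypothesis is a percentage in 10 or 20 patients.** Uptake has eligible patients as its denominator, and the protocol's Feasibility Hypothesis 1 is a count of 20 enrolled.
- **A met threshold is compatible with plain infeasibility.** No infeasible rate is defined. A lower limit of 56% for assessment is well below 80%, but whether it is unworkable is a matter of judgement.
- **The thresholds are a go/no-go rule, or the percentages will be read as exact.** No such rule is stated. The text shows only that no measure of uncertainty is planned.

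The sample is also a convenience sample (protocol section 7), so an interval covers sampling error only.

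**Conclusion.** The point holds as a limited one about reporting. Three thresholds are set as hypotheses, and no interval is planned for any of them. A result exactly at threshold leaves an exact lower limit about 34 percentage points below the observed rate for session completion (60 − 26.2 = 33.8), 24 for assessment (80 − 56.3 = 23.7) and 16 for uptake (50 − 33.8 = 16.2).

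The adherence and assessment intervals rest only on the documents' own counts, taking all 20 randomized as the assessment denominator. The uptake interval assumes 40 eligible patients. The tail probabilities depend on assumed true rates and should be read across their range. The trial's conduct and sample size are unaffected; what changes is how firmly the pilot can speak to planning the larger trial.

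**What to change.** 1. Reconcile the adherence definitions across the documents, so that the interval has one defined target: the SAP's 6 of 10 with at least 3 of 5 sessions, the SAP's secondary endpoint of all 5 sessions, and the protocol's 7 of 10 with at least 4 of 5 visits.
2. In the SAP paragraph on feasibility outcomes, state that uptake, 1-month completion and session adherence will each be reported with numerator, denominator and exact (Clopper-Pearson) 95% confidence interval. Name uptake explicitly: it is the listed primary feasibility endpoint, but that paragraph does not mention it.
3. Add that meeting a threshold describes this sample, and that the interval will inform planning of the larger trial.

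Beyond the reconciliation, the cost is a short addition to the SAP and one table column. The downside is that the feasibility results will read less favourably.
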